11.5.2.5 Time Course Analysis

Time course analysis will compare time course of the response up to Visit 5 (Year 5) using MMRM (Mixed Model Repeated Measure) procedure. The change from baseline in the LogMAR and change from baseline in log of contrast sensitivity (LogCS) will be the responses. The change from baseline of all-GS010 eyes will be compared to the change from baseline of all-sham eyes using a MMRM including the subject and the eyes of the subject as random factors, the treatment, follow-up visit, eye status at baseline (better or worse), interaction between baseline values and treatment, interaction between linear time from onset of disease and treatment, interaction between eye status at baseline and treatment, interaction between linear time and treatment and baseline LogMAR as predictors in the model. The estimate of treatment effect at various follow-up time points and its 95% confidence interval (CI) (without adjustment for multiplicity) will be presented. Compound symmetry structure will be fitted. In case of any convergence problem with this covariance structure, other covariance structures will be used.

Time course analysis of Humphrey visual field parameters and SD-OCT parameters will be conducted similarly to the time course analysis of LogMAR (details will be provided in the SAP).

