11.5.6 Handling of Missing Data

In case of missing data, the imputation methods are described as follows:

Safety

Missing/partial start date and missing/partial end date for all TEAEs will be imputed. The rules will be detailed in the SAP.

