5.5 HANDLING OF MISSING DATA AND/OR INVALID DATA AND OUTLIERS

5.5.1 Efficacy

In case of missing data, the following rules will be applied as a primary imputation method applicable to all visits of interest (follow-up study time points 2, 2.5, 3, 4 and 5 years):

For all analysis timepoints, a review of the visits with available BCVA value will be done by GenSight to decide, for each patient, which visit will be used for this specific timepoint analysis. The document will be provided in excel format, and then imported in SAS in order for the statistician to perform the analysis (CLIN-06_DRM_Listings_V1.0_30JUN2022).

If Year-2 visit is not available at Clin06 inclusion, then “Follow-up Visit 12” (corresponding to Week 96) from Clin03A/Clin03B will be used.

After this affectation, in case of missing LogMAR value at a visit, LOCF will be applied with all analysed visits.

When a test result score/value for the Pelli-Robson Contrast test is missing at any visit for the reason that the subject was unable to perform because the vision was too poor, the following convention will be used: the worst possible score for the given test will be assigned as the value for that visit (i.e., 0 LogCS).

The imputation method of missing data used in each analysis will be specified in the TFLs in a footnote.

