6.2 MODIFIED INTENT-TO-TREAT

The Modified Intent-to-Treat (mITT) Population is defined as those subjects who received study medication in RESCUE or REVERSE Phase III studies, consented to be enrolled in this long-term follow-up study, and provide visual acuity data at Visit 2. This population will be used as the primary population for efficacy and QoL analyses. This population is identical to the Safety Population. Missing non-safety endpoints will be imputed with LOCF.

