6.3 PER PROTOCOL

The Per Protocol (PP) Population is the subset of mITT who completed the follow-up study, and have data available at scheduled/unscheduled (within the allowable time window) visit. This population will be used as the for supportive efficacy and QoL analyses. Missing data will not be imputed.

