8.7 EXPLORATORY ANALYSES

8.7.1 Exploratory efficacy analyses

As an exploratory analysis, the response to treatment through Visit 5 (Year 5) using a MMRM model will be performed. The change from baseline in the LogMAR will be the response. Change from baseline of all-GS010 eyes will be compared to the change from baseline of all-sham eyes. The model will include subject as a random factor and fixed effects for treatment, follow-up visit (time point), eye status at baseline (better or worse), time from onset of disease and LogMAR at baseline as a covariate. The following interactions will be explored: baseline LogMAR and treatment; time from onset of disease and treatment; and eye status at baseline and treatment. The estimate of treatment effect at various follow-up time points and its 95% confidence interval (CI) will be presented. A UN@AR(1) (Autoregressive(1)) covariance structure will be fit to accommodate the doubly repeated measures data (repeated over time and eye). In the event of convergence problems with this covariance structure, other covariance structures will be explored.

Time course analysis of log of contrast sensitivity (LogCS), Humphrey visual field parameters and SD-OCT parameters will be conducted similarly to the time course analysis of LogMAR.

Other exploratory analyses will be performed for all analysed visits as a sensitivity analysis, excluding off-chart evaluations whose distance to the subject was superior to 2 meters. The endpoints analysed will be the ones described in 8.5.2.2 at eye level.

Additional exploratory analyses may be performed in the study.

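### LOCF is the primary rule for missing LogMAR, which matters at Years 3 to 5; the exploratory MMRM that could check it lists no treatment-by-visit term and does not state its input data

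*SAP*

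**What the plan says.** **Imputation.** SAP 5.5.1 describes its rules as the primary method for all follow-up time points. For acuity: "After this affectation, in case of missing LogMAR value at a visit, LOCF will be applied with all analysed visits". SAP 6.2 widens this for the mITT: "Missing non-safety endpoints will be imputed with LOCF". The EMA and FDA LogMAR analyses in SAP 8.5.2.2 both use the mITT.

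**Where it applies.** Year 2 can be filled from the parent study's Week 96 visit (SAP 5.5.1). Year 2.5 should be present because mITT members must have consented "and provide visual acuity data at Visit 2". That leaves Years 3, 4 and 5. SAP 6.2 also calls the mITT identical to the Safety Population; if that statement governs, Year 2.5 could be carried forward as well.

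**Protocol on missing data.** Section 11.5.6 opens with "In case of missing data, the imputation methods are described as follows", but the only rule that follows concerns adverse event dates.

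**Non-imputed analysis.** SAP 8.5 repeats all efficacy analyses in the Per Protocol population, without imputation. That population is the "subset of mITT who completed the follow-up study, and have data available at scheduled/unscheduled (within the allowable time window) visit".

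**MMRM.** SAP 8.7.1 has treatment and visit as main effects, with eye status, time from onset and baseline LogMAR. On interactions: "The following interactions will be explored: baseline LogMAR and treatment; time from onset of disease and treatment; and eye status at baseline and treatment". It then promises treatment effects at various time points. Protocol 11.5.2.5 listed a further term: "interaction between linear time and treatment and baseline LogMAR as predictors in the model". SAP 8.8 reports the new covariance structure and the exploratory status of the time-course models, but not the removal of that term.

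**The concern.** LOCF supplies, for each missing subject, the answer that the follow-up is meant to find: no change since the last value. Under random dropout, a real late change in the GS010-sham contrast is shrunk in proportion to the share of carried values. Equal change in both eyes cancels in the contrast.

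The usual safeguard is a second analysis that makes a different assumption about the missing values. Per Protocol cannot do this, because it drops the people who left. The MMRM could, but two points are open. If it runs on mITT data already filled under SAP 6.2, it inherits the LOCF assumption. If its fixed effects are only those listed, it cannot show a treatment effect that changes between visits. At stake is what the report can say about durability at Years 3 to 5.

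**Working it through.** The documents give no number of subjects, SD, expected effect or dropout rate, so there is no planned figure to reproduce. Everything below is illustrative.

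**Assumed inputs.** Benefit e = 0.15 LogMAR (half the 0.3 responder threshold) at Years 2, 2.5 and 3, then 0.075 at Year 4 and 0 at Year 5. Missing share at Year 5: m = 0.1, 0.2, 0.3. Last observed values are split evenly over Years 2.5, 3 and 4. One letter = 0.02 LogMAR (Protocol 9.6.5).

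**1. LOCF, dropout unrelated to outcome.**
- Year 5 bias = m × (0.15 + 0.15 + 0.075)/3 = 0.125m = 0.013, 0.025, 0.038 LogMAR (0.6, 1.3, 1.9 letters). The truth is 0.
- Year 4 bias = (2m/3) × (0.15 − 0.075) = 0.05m = 0.005, 0.010, 0.015.
- Half the loss gives half the bias. A late gain of the same size gives the same bias with opposite sign. A stable effect gives zero.

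**2. LOCF, dropout related to outcome (simulated).** 60 subjects, within-subject eye contrast with SD 0.35, between-visit correlation 0.85, visits at Years 2.5, 3, 4 and 5. Entries are Year 5 bias in GS010 minus sham at 10%, 20%, 30% missing; a negative value favours GS010.

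| Dropout driven by | Late loss | Stable effect | Late gain |
|---|---|---|---|
| Last observed contrast | −0.009, −0.016, −0.028 | +0.004, +0.008, +0.015 | +0.017, +0.035, +0.050 |
| Current unseen contrast | −0.015, −0.029, −0.044 | 0.000, −0.003, −0.006 | +0.010, +0.022, +0.036 |

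In the first row a likelihood estimate with a free mean at each visit stays within 0.002, while plain observed means are off by about −0.03, −0.06, −0.085. In the second row the likelihood estimate is off by −0.003 to −0.017; with a stable effect and 30% missing, LOCF is closer (−0.006 against −0.017). For the first row, other correlation values and structures change the sizes but not the signs.

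**3. The MMRM with the terms as listed, complete data.** With treatment and visit as main effects only, the model fits one difference δ, a weighted mean of e over Years 2, 2.5, 3, 4 and 5.
- Equal weights: δ = (0.15 + 0.15 + 0.15 + 0.075 + 0)/5 = 0.105.
- AR(1) weights in visit order (1 for the first and last visit, 1 − r for the others): δ = [0.15 + (1 − r) × 0.375] / [2 + 3(1 − r)].
 - r = 0.80: 0.225/2.60 = 0.087
 - r = 0.85: 0.20625/2.45 = 0.084
 - r = 0.90: 0.1875/2.30 = 0.082

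So the model reports about 0.08 to 0.105 at every visit, against a truth of 0.15 at Year 3 and 0 at Year 5. The three listed interactions do not help if their covariates are fixed per subject or eye. SAP 4.4 and 5.4 describe duration of vision loss at the time of treatment, which is fixed. Only a time from onset that advances with each visit would let the effect drift.

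**4. Cross-check with another scenario.** True difference −0.30 at Year 2, moving linearly to 0 at Year 5, 30% random dropout, random subject intercept in place of UN@AR(1), 150 runs:

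| Analysis | Year 5 estimate (truth 0) |
|---|---|
| LOCF | −0.053 |
| Listed MMRM, observed data | −0.180 (same at all visits) |
| With treatment-by-visit, observed data | 0.002 |
| With treatment-by-visit, LOCF-filled data | −0.052 |

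Both corrections are needed: the term without observed data reproduces the LOCF answer.

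**The case against.** **The MMRM text may only be loosely worded.** It promises effects by time point, which implies some time-by-treatment term, and SAP 8.8 calls the model building exploratory. That is fair: the pooled-difference result holds only on a literal reading. But the protocol had such a term and the SAP list does not, so the intention should be written down.

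**The LOCF bias is modest.** This stands. It needs a late change in the contrast or outcome-related dropout. Early termination visits carry the full Year 5 assessments (Protocol 8.7) and may shorten the gap. The natural-history study described in Protocol 5.1 found no significant acuity change to 36 months, which gives some support for stability in untreated eyes, though not in treated ones. SAP 8.1 reports missing counts, and 5.5.1 adds: "The imputation method of missing data used in each analysis will be specified in the TFLs in a footnote". These disclose the handling but do not test it.

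**Readings that go too far.** A reader might infer any of the following; the documents do not support them.
- *MMRM should replace the main analysis.* Protocol 11.5.2.2 and secondary endpoint 8 name ANCOVA, and no best-eye MMRM is planned. UN@AR(1) at unequally spaced visits, with assigned off-chart values of 2, 2.3, 4 and 4.5 (SAP 5.4), is not clearly the better main model. The calculations above cover only the all-eye contrast.
- *LOCF favours GS010.* Its direction depends on the late course and on who drops out.
- *LOCF breaches the protocol.* Protocol 11.5.6 has no efficacy rule, and 11.2 leaves data handling to the SAP.
- *The sponsor may pick visits freely.* SAP 5.5.1 has the sponsor choose each patient's visit for each time point and states no date rule there. SAP 6.3 refers to an allowable window, and a rule may lie in text not available for this review. This warrants a clarification request and is not part of the finding.

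**Conclusion.** The point holds in a limited form. LOCF is the primary rule for missing LogMAR, the only stated non-imputed analysis is restricted to completers, and the MMRM as written is not yet a usable check. The clearer defect is in the MMRM. On its listed terms, and unless time from onset varies by visit, it cannot show a changing effect even with nothing missing (about 0.08 to 0.105 at every visit in the assumed example). The LOCF bias is secondary: about 0.013 to 0.038 LogMAR at Year 5 under 10% to 30% random missingness and full loss of a 0.15 effect, zero with a stable effect and dropout unrelated to outcome, and variable in size and sign otherwise. The effect size, missing shares, SD and correlations are all assumptions. The primary endpoint is safety and is untouched. This should be fixed, but it does not undermine the study.

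**What to change.** 1. In SAP 8.7.1, add categorical treatment-by-visit as a fixed term, and state that the model uses observed, non-imputed LogMAR from all enrolled subjects.
2. Present its all-eye estimates for Years 3, 4 and 5 beside the LOCF ANCOVA as a named sensitivity analysis. Base statements on durability or late change on both.
3. Keep the protocol's ANCOVA as the main EMA and FDA model. If a matching best-eye check is wanted, add it as a new between-subject MMRM.
4. Do not use per-visit ANCOVA on observed values instead: at Year 5 it is close to a completer analysis and can be more biased than LOCF (working, step 2).
5. Record in SAP 8.8 that the protocol's linear time-by-treatment term was dropped and what replaces it.

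The cost is SAP wording and modest programming on a model already planned; a best-eye MMRM would be extra work. Late-visit intervals widen somewhat. Using SE ratio (LOCF to MMRM) = 1/√[r² + (1 − r²)/(1 − m)] with r = 0.8 to 0.9, LOCF standard errors are 1–2%, 2–4% and 4–7% smaller than the MMRM's at 10%, 20% and 30% missing. The MMRM still assumes that dropout depends only on observed data, so it complements LOCF and does not settle the question.

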5.5.2 Safety

Missing/partial start date and missing/partial end date for all TEAEs will be imputed.

Missing/Partial Start Date for AEs

The following rules will be applied to missing or incomplete start dates when determining if an AE is treatment emergent. The rules will be applied first before determining the treatment emergent status and imputed dates will be treated as complete dates for this purpose. These rules are intended to lead to a conservative assessment of treatment emergence. The imputed dates are only used for determining treatment emergence and the recorded partial dates will be displayed in listings. The same rules will be applied for prior and concomitant medications as per [Section 5.4](#).

If the year of onset of the AE is missing, then the AE is considered treatment emergent.

If the year of the AE onset date is complete, but the month and day of the onset of the AE are missing, then the following rules apply:

- If the year of the AE is the same as the year of the study treatment administration then the AE is considered treatment emergent, and the AE onset date will be set to the study treatment administration date.
- If the year of the AE onset date is after the year of study treatment administration, then the date is set to 01 January and the AE is considered treatment emergent.
- If the year of the AE onset date is before the year of study treatment administration date, then the AE is not treatment emergent.

If the year and month of the AE onset date are complete, but the day of the onset of the AE is missing, then the following rules apply:

- If the year and month of the AE onset date is the same as the year and month of the treatment administration date, then the AE is considered treatment emergent and the AE onset date will be set to the treatment administration date.
- If the year and the month of the AE onset date are complete, and the month of the AE onset date is after the month of the study treatment administration date, then the day of the AE

onset date will be set to the first day of the month. The AE will be assigned as treatment emergent.

- If the year and the month of the AE onset date are before the year and the month of treatment administration date, then the AE is not treatment emergent.

Missing/Partial End Date for AEs

If the end date is missing and the start date is on or after the date of treatment administration, then the AE is considered treatment emergent.

6. ANALYSIS SETS

6.1 SAFETY

The Safety Population is defined as those subjects who received study medication in RESCUE or REVERSE Phase III studies and consented to be enrolled in this long-term follow-up study. This population will be used as the population for all safety analyses.

6.2 MODIFIED INTENT-TO-TREAT

The Modified Intent-to-Treat (mITT) Population is defined as those subjects who received study medication in RESCUE or REVERSE Phase III studies, consented to be enrolled in this long-term follow-up study, and provide visual acuity data at Visit 2. This population will be used as the primary population for efficacy and QoL analyses. This population is identical to the Safety Population. Missing non-safety endpoints will be imputed with LOCF.

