11.4.2 Intent-to-treat Population

The intent-to-treat population will be defined as all subjects who received study medication in RESCUE or REVERSE Phase III studies and consented to be enrolled in this long-term follow-up study. This population will be used as the population for efficacy and QOL analyses. This

population is identical to the safety population.

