3.2 DURATION AND SCHEDULE OF STUDY PARTICIPATION

Study Duration

Total study follow-up is 3 years and the study will end with the last subject's last visit. The estimated total length of the subject follow-up is 5 years after the initial IMP administration.

Study Schedule

The follow-up study is divided into the following visits:

Visit 1: Inclusion Period (Year 2)

The Inclusion Period starts on the date of last visit (Week 96) of the RESCUE/REVERSE study and ends 1 day prior to Visit 2 (Year 2.5, Day 180 post Week 96 (Visit 12 of CLIN-03)) of the long-term follow-up study.

It is preferable for Visit 1 to be combined with Week 96/EOS visit of RESCUE/REVERSE study, but if not possible this can be a separate visit during the Inclusion Period. During this Period the informed consent is signed, eligibility criteria, adverse events (AEs)/ serious adverse events (SAEs) and concomitant medications (CMs) are reviewed and any other assessments needed that were not performed during the Week 96/EOS visit of RESCUE/REVERSE are completed.

Physical examinations including vital signs, electrocardiogram, laboratory assessments, quality of life, and ocular and vision assessments will also be done. A review of medical, surgical and prior medication history will also be performed.

Visit 2: Year 2.5 (\pm 4 Weeks) Post-treatment

During this visit, concomitant medications are reviewed, along with AEs and SAEs, and Ocular and Vision Assessments are carried out.

Visit 3: Year 3 (\pm 4 Weeks) Post-treatment

During this visit, assessments from Visit 2 are repeated and additional quality-of-life and Pelli-Robson contrast sensitivity assessments are carried out.

Visit 4: Year 4 (\pm 4 Weeks) Post-treatment

All assessments from Visit 3 are repeated during this visit.

Visit 5: Year 5 (\pm 4 Weeks) Post-treatment (EOS) or Early Termination Visit (ETV)

Assessments from Visit 4 are repeated. Additional physical examination including vital signs, electrocardiogram, and laboratory assessments, are performed.

Unscheduled Visit

Unscheduled visits can be performed anytime to assess or monitor AEs, or at the subject's or investigator's request. The date and reason for the unscheduled visit should be recorded in the source documents.

The study plan and assessments are shown in Protocol Section 8.2, Table 1: Schedule of Events of the protocol.

Sponsor: GenSight Biologics
 Protocol No: GS-LHON-CLIN-06

Statistical Analysis Plan
 Final Version 2.0 / 30-June-2022

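### SAP 6.2 makes Visit 2 visual acuity a condition of the mITT set, yet calls that set identical to the Safety Population, and 8.8 does not list the departure from the protocol's ITT

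*SAP*

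**What the plan says.** SAP 6.1 gives the Safety Population this definition: "those subjects who received study medication in RESCUE or REVERSE Phase III studies and consented to be enrolled in this long-term follow-up study". Treatment and consent are the only conditions.

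SAP 6.2 defines the mITT set with the same two conditions and adds a third. Members must have "consented to be enrolled in this long-term follow-up study, and provide visual acuity data at Visit 2". On its use it says: "This population will be used as the primary population for efficacy and QoL analyses". The next sentence reads: "This population is identical to the Safety Population". The section ends by calling for LOCF on missing non-safety endpoints.

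Protocol 11.4.2 has an ITT set instead, with this definition: "all subjects who received study medication in RESCUE or REVERSE Phase III studies and consented to be enrolled in this long-term follow-up study". The protocol adds that the "population is identical to the safety population". Protocol 11.5.2.2 runs both the EMA and the FDA LogMAR analyses on ITT. SAP 8.5.2.2 runs both on mITT.

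SAP 8.8 lists the changes from the protocol. On populations it names two: the pediatric and subset populations, said to come on top of those in the protocol, and the Per Protocol set. It mentions neither the replacement of ITT by mITT nor the Visit 2 condition. SAP section 6 defines no ITT set.

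**The concern.** The definition of mITT and the sentence equating it with Safety can describe different sets, and nothing in 6.2 says which governs. Two programmers working from this section could build different primary efficacy populations.

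The added condition also depends on what happens after enrolment. Under SAP 3.2 the Inclusion Period starts at Week 96 "and ends 1 day prior to Visit 2 (Year 2.5, Day 180 post Week 96". Every subject is therefore enrolled before Visit 2 takes place, and one who withdraws or misses that visit would be removed retrospectively. Year 2 results would then depend on attendance about half a year later. Quality of life and contrast sensitivity would depend on a visit at which neither is measured: SAP 3.2 introduces them only at Visit 3, where "assessments from Visit 2 are repeated and additional quality-of-life and Pelli-Robson contrast sensitivity assessments are carried out".

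No other efficacy set offers an unselected check. The Per Protocol set is a subset of mITT, and the best-eye and worst-eye subsets are taken from mITT and Per Protocol (SAP 6.3, 6.4). A reader who relies on 8.8 to learn where the SAP departs from the protocol would not find this departure.

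**Working it through.** The plan gives no figure to reproduce, so the check compares definitions and then counts scheduled time points.

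**Set definitions**

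| Set | Source | Treated | Consented | Visit 2 acuity |
|---|---|---|---|---|
| Safety | SAP 6.1 | yes | yes | not required |
| ITT | Protocol 11.4.2 | yes | yes | not required |
| mITT | SAP 6.2 | yes | yes | required |

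Let N be the number of treated and consented subjects, and m the number of those without visual acuity at Visit 2. Then:

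- Safety = N
- protocol ITT = N
- SAP mITT, by its definition, = N − m

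The identity stated in 6.2 needs N − m = N, that is m = 0. In the protocol the corresponding identity holds by definition, because ITT and Safety have the same conditions. In the SAP it becomes a claim about the data. Neither N nor m appears in the documents.

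**Can m exceed zero?** The definitions allow it, because consent precedes Visit 2. Protocol 7.3.3 provides for withdrawal and loss to follow-up without replacement. SAP 5.5.1 plans LOCF for missing LogMAR at all analysed time points, Year 2.5 included. SAP 8.1 plans counts of missed visits and of missing visual acuity. The plan therefore expects that such values can be missing.

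**What one affected subject would lose.** Take a subject who lacks only Visit 2 acuity, and suppose the condition is applied.

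| Endpoint | Time points in the SAP | Scheduled | At Visit 2 | Collected but excluded |
|---|---|---|---|---|
| LogMAR (8.5.2.2) | Years 2, 2.5, 3, 4, 5 | 5 | 1 | 5 − 1 = 4 of 5 |
| Contrast sensitivity (8.5.2.1) | Years 2, 3, 4, 5 | 4 | 0 | 4 − 0 = 4 of 4 |
| VFQ-25 and SF-36 (8.5.2.6) | Years 2, 3, 4, 5 | 4 | 0 | 4 − 0 = 4 of 4 |

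These are upper limits, since such a subject may miss other visits too. If the identity sentence is applied instead, none of these data are lost.

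**Disclosure.** The items of SAP 8.8 were read in full. The only population items are the pediatric and subset populations and the Per Protocol set.

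**The case against.** The strongest reply is that the identity sentence records an observed fact. The SAP is Final Version 2.0 of 30 June 2022, the same date as the data review listings cited in 5.5.1. It describes enrolment in the past tense, and 8.8 reports that Year 2.5 quality-of-life data were not collected. Visit 2 was probably complete and reviewed when 6.2 was finalised. If every enrolled subject had the value, m = 0, mITT equals the protocol's ITT, and the omission from 8.8 is only an unlisted name and definition. This is possible, but the SAP does not say so, and nearly the same sentence stands in the protocol, where it needs no data to be true.

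Second, SAP 5.5.1 lets the sponsor decide, subject by subject, which visit serves each time point before LOCF is applied. A subject without acuity at the nominal Year 2.5 visit might therefore still count as having it. That rule allocates values to time points and does not define membership of mITT. It does leave open how strictly the condition would be read, which is why the losses above are stated as upper limits.

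Third, Visit 2 may be a slip for the Year 2 visit. SAP 3.2 and its schedule label Year 2.5 as Visit 2, so this is not the literal reading. It would still add an unlisted condition that the Safety definition lacks.

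Fourth, each subject has one GS010 eye and one sham eye, so in the all-eyes comparison an exclusion removes a matched pair. That stands. In the best-eye and worst-eye comparisons the two arms come from different subjects, so an exclusion removes an eye from one arm only.

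Finally, the separate Safety and mITT counts in 8.1 do not show that the sets differ. They would reveal a difference once the tables are produced. They would not settle beforehand which sentence of 6.2 applies.

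**Conclusion.** The concern holds. As written, SAP 6.2 gives two descriptions of the primary efficacy and quality-of-life set that coincide only if m = 0, and the SAP neither states nor ensures that. The definition brings in a post-enrolment selection rule that the protocol's ITT does not have, and 8.8 does not report it.

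The numerical effect cannot be calculated, because N and m are not given, and it may be nil. The per-subject loss of up to 4 of 5, 4 of 4 and 4 of 4 time points assumes that the condition is applied to the nominal Visit 2 and that only that acuity value is missing. SAP 8.5.4 makes all efficacy analyses secondary, and the primary safety analysis uses the Safety Population, so it is unaffected. This should be fixed, but it does not threaten the study's primary objective.

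**What to change.** Delete the Visit 2 acuity condition from SAP 6.2. The set then matches the protocol's ITT, and the identity with Safety is true by definition. Call it ITT as the protocol does, or keep the name mITT and note the renaming in 8.8.

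If the sponsor wants a set restricted to subjects with Visit 2 acuity, define it as a named sensitivity set without the identity sentence, and list it in 8.8.

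The cost is one clause and one population flag, plus one line in 8.8 if the new name or a Visit 2 subset is kept. No new data or tables are needed, since 8.1 already plans the Safety and mITT counts, visit attendance and missing visual acuity. If every enrolled subject has the Visit 2 value, the change alters no result.
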